2.1 Primary estimands

The primary clinical question of interest is: What is the probability that a positive [¹⁸F]CTT1057 PET/CT scan truly detects and localizes (PSMA-expressing) tumor recurrence in BCR PCa patients?

The justification for the primary estimand is that we wish to assess the diagnostic performance of [18F]CTT1057 PET/CT in detecting and localizing PSMA positivity in PCa patients diagnosed of biochemical recurrence (BCR), which represents a stage of PCa where there is an increase in PSA levels after initial treatment. Correct identification of disease location and extent guides treatment decisions. It is relevant, therefore, to detect smaller lesions as early as possible. Sensitivity and specificity of [18F]CTT1057 PET/CT in detecting and localizing PSMA positivity using histopathology as SoT will be assessed in an independent study in newly diagnosed high-risk PCa patients candidate to surgery. However, in this primary staging population a low prevalence and high variability of metastatic lymph nodes has been reported (from 4-58%) (Petersen and Zacho 2020). Therefore, an additional study in the BCR setting is needed, since this is a relevant patient population which is expected to have an adequate representation of metastasis-positive and metastasis-negative patients by any available reference standard. In this population, a CTS is needed for reference (for CTS details see Section 3 and Section 4.1). Pathology is available in only a limited number of cases, and morphological imaging is negative in a substantial number of cases. This makes the identification of true and false negative results a challenge, thus complicating the evaluation of sensitivity and specificity. Therefore, the region-level correct localization rate (CLR) defined as the region-level PPV with anatomical localization and the patient-level PPV with anatomical localization are more appropriate co-primary endpoints than sensitivity and specificity in the BCR setting. The patient-level PPV with anatomical localization, as the conditional probability of positivity given the result of the PET/CT scan is more meaningful than the correct detection rate (CDR) defined as the percentage of true-positive patients in the whole population

Amended Protocol (Version No. 01 Clean)

(unconditional probability of positivity). Moreover, the CDR has reported to be dependent of the PSA levels in the BCR population using another [18F]-PSMA labeled PET agent (Chantadisai et al 2020).

The primary estimands are described by the following attributes:

Primary estimand 1:

- 1. Population: Patients with biopsy proven prostate adenocarcinoma and rising PSA after definitive therapy with RP or curative-intent radiation therapy (external beam or brachytherapy), diagnosed of biochemically recurrent PCa. Further details about the population are provided in Section 5.
- 2. Variable: Proportion of regions containing at least one TP lesion (anatomically localized correspondence between [18F]CTT1057 PET imaging and the reference standard), regardless of any co-existent FP findings within the same region, out of all regions containing at least one [18F]CTT1057 PET-positive finding, using central readings
- 3. Treatment of interest: [18F]CTT1057 injected as a single intravenous dose of approximately 370 MBq and subsequent PET/CT scan. Further details about the investigational treatment is provided in Section 6.
- 4. Handling of remaining intercurrent events: Patients who received the investigational imaging agent [18F]CTT1057 but did not undergo/complete the PET scan for any reasons (e.g. consent withdrawal, PET camera failures, etc.) Details on how to handle intercurrent events are provided in Section 12.4.3.
- 5. Summary measure: Estimate of proportion of regions containing at least one TP lesion (anatomically localized correspondence between [18F]CTT1057 PET imaging and the reference standard), regardless of any co-existent FP findings within the same region, out of all regions containing at least one [18F]CTT1057 PET-positive finding (CLR) and CLR along with 95% CI estimated using logistic random-effects models taking into account the correlation among regions within one patient.

Primary estimand 2:

- 1. Population: the same as primary estimand 1
- 2. Variable: Proportion of patients who have at least one TP lesion (anatomically localized correspondence between [18F]CTT1057 PET imaging and the reference standard), regardless of any co-existent FP findings, out of all PET positive patients, using central readings.
- 3. Treatment of interest: the same as primary estimand 1
- 4. Handling of remaining of intercurrent events: the same as primary estimand 1
- 5. Summary measure: Estimate of proportion of patients who have at least one TP lesion (anatomically localized correspondence between [18F]CTT1057 PET imaging and the reference standard), regardless of any co-existent FP findings, out of all patients who are PET/CT scan positive (PPV) and PPV along with 95% CI estimated using binomial distribution.

Protocol No. CAAA405A12301

2.2 Secondary estimands

Not applicable

3 Study design

This is a prospective, open-label, multi center, single-arm Phase III study to evaluate the diagnostic performance of [18F]CTT1057 as a PET imaging agent for detection and localization of PSMA positive tumors in PCa patients diagnosed with biochemical recurrence (BCR) after initial definitive therapy with either RP or curative-intent RT, using a CTS as reference.

Approximately 190 participants will be enrolled to ensure at least 152 participants are evaluable for the co-primary endpoints. [18F]CTT1057 PET/CT scan imaging will be read in a central Contract Research Organization (CRO) by 3 independent nuclear medicine physicians who will be blinded to any other patient data. See Section 4.1 and Section 8.3.1 for central read details.

The CTS to be used as reference will be hierarchical in nature, with 3 levels of SoT procedures that will be applied as follows:

Level 1)

• **Histopathology** if available for a lesion (from prospective biopsy or salvage surgery performed within 8 weeks after the [¹⁸F]CTT1057 PET/CT scan); OR in case that histopathology is not available for a lesion, inconclusive (i.e. if biopsy/surgery tissue sample is not evaluable for histopathology assessment due to sample quality or inadequate quantity or any other technical causes) or negative (for biopsy only):

Level 2)

• Imaging diagnostic procedures performed on each patient as clinically indicated per SoC, which must include the [68Ga]Ga-PSMA-11 PET/CT scan that is mandatory for all subjects randomized in the study and at least a high resolution CT scan (covering at least chest, abdomen, and pelvis and any other region as clinically indicated) with intravenous and oral contrast (or MRI if CT scan with contrast is medically contraindicated). The high resolution CT scan and any other imaging diagnostic procedure clinically indicated as per SoC must be acquired within the 8 weeks either prior to or following the [18F]CTT1057 PET/CT scan. Three-month follow-up imaging (from baseline) will also be used as part of the CTS level 2 in cases where it is clinically required for the diagnosis of particular lesion(s); OR if neither of the two above are feasible or deemed appropriate or they are inconclusive (i.e. images are not interpretable due to poor or inadequate image quality that precludes reliable assessment):

Level 3)

• 50% or greater decline in **PSA following radiation therapy** (as long as no concomitant androgen deprivation therapy (ADT) is given) as per PCWG3 criteria (Scher et al 2016).

In the cases where pathology will be available, assessments by the local pathologists will be performed as per SoC, and results should be available within 2 weeks after surgery. Pathologists will be blinded to any PSMA-PET data (i.e. both PET/CT scans). In this case, only pathology will be used as SoT for the concerned lesion(s).

In the cases where pathology will not be available for a lesion, the central read results of the [68Ga]Ga-PSMA-11 PET/CT scan (performed for all subjects randomized) and other imaging diagnostic procedures to be performed on each participant for the CTS level 2 will be used as SoT for the co-primary endpoint calculations. See Section 4.1 for central read details.

[figure not shown]
All patients will undergo a [⁶⁸Ga]Ga-PSMA-11 PET/CT as part of the study, for both the CTS Level 2 (in case it is required as SoT) and the secondary endpoint of assessment of concordance between [¹⁸F]CTT1057 and [⁶⁸Ga]Ga-PSMA-11 for detection of lesions (as detailed in Section 2).

In addition to central review, local review of SoC images (including [⁶⁸Ga]Ga-PSMA-11) will be performed to be used by the treating physician/Clinical Study Investigator for patient management decisions and overall assessment.

See Section 8.3.1 for assessment details and Section 6.4 for blinding requirements.

A questionnaire on the planned patient management will be filled-in by the treating physician/Clinical Study Investigator before (questionnaire 1) and within 14 days after (questionnaire 2) knowing the results of the [18F]CTT1057 PET/CT scan. A local review of [18F]CTT1057 PET/CT images will also be performed by a local nuclear medicine physician or radiologist with expertise in reading oncology PET/CT scans and the results will be provided to the treating physician/Clinical Study Investigator for completion of questionnaire 2. Options will be given in the questionnaire to capture possible management plan, such as Surgery, Radiation alone, Radiation alone with change in radiation treatment plan (only applicable for questionnaire 2), Radiation plus ADT, ADT alone, Observation/surveillance, Other (free text box). Any change in patient management plan between the questionnaire 1 and questionnaire 2 should not be based only on [18F]CTT1057 PET/CT scan results since this is an investigational diagnostic imaging product. Other diagnostic procedures should be performed as per SoC in order to confirm and implement the changed management plan. See Figure 3-1 for study design schema.

Figure 3-1 Study Design

Screening period

Written informed consent form (ICF) must be obtained prior to any screening procedures. The participant must be registered in the Interactive Response Technology (IRT) for screening. All procedures described in the Assessment Schedule as per Table 8-1 must be carried out, prioritizing laboratory assessments to allow time to obtain the results at least 14 days prior the planned first PET imaging day (Day 1). Eligibility must then be confirmed at the latest on Day -14. The screening period should last up to 28 days.

Once eligibility is confirmed, the participants will be randomized in IRT to be assigned to one of the following two PET/CT scan sequences at random in a 1:1 ratio:

- Sequence 1: [¹⁸F]CTT1057 on Day 1 (investigational imaging agent of interest) followed by [⁶⁸Ga]Ga-PSMA-11 at least 14 days apart (as part of CTS if required, and for secondary endpoint)
- Sequence 2: [⁶⁸Ga]Ga-PSMA-11 (as part of CTS if required, and for secondary endpoint) on Day 1 followed by [¹⁸F]CTT1057 (investigational imaging agent of interest) at least 14 days apart

PET Imaging days

The 2 PET imaging procedures will be done at least 14 days apart. The day of the first PET imaging agent injection will be considered study Day 1. Please refer to Section 8.3.1 for the steps that will take place on each PET imaging day.

Both visits will also be considered as the End of Treatment (EOT) visits.

Safety Checks

All treated participants will be contacted by phone within 24 to 72 hours following each PET/CT scan in order to capture potential occurring Adverse Events.

Safety Follow-up

Participants will come back to the hospital 14 days (+ 3 day window) after each PET/CT scan day, for a safety visit including vital signs, lab and urine analysis. For participants undergoing surgery, radiation therapy or initiating any antineoplastic medication (provided all CTS procedures have been completed before this initiation) prior to planned safety visit, these safety follow-up assessments will need to be performed before the surgery/radiation therapy/initiation of antineoplastic medication.

Additional Follow-up

Additional follow up period will be applicable where additional diagnostic procedures are to be performed. These may include SoC pathology, imaging or other modality disease assessments (CTS Levels 1 or 2) up to 8 weeks after [¹⁸F]CTT1057 PET/CT scan or three-month follow-up imaging (from baseline) where it is clinically required for the diagnosis of particular lesion(s).

In addition, in cases where the CTS Level 2 is not feasible/appropriate or inconclusive, and the CTS Level 3 will apply and will include the assessment of PSA levels prior to starting RT (which should commence within 8 weeks of completing [18F]CTT1057 PET/CT scan) and at approximately 90 days from last day of radiation.

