Evaluate detection rate	 Proportion of patients who have at least one PET positive lesion, regardless of TP or FP findings, out of all patients who are scanned 		
Evaluate the region level sensitivity of [18F]CTT1057	 Proportion of regions that test positive on both [18F]CTT1057 and CTS (TP) among those regions that are CTS positive (TP or FN) 		
Evaluate the region level specificity of [18F]CTT1057	Proportion of regions that test negative on both [18F]CTT1057 and CTS (TN) among those regions that are CTS negative (FP, or TN)		
Evaluate the region level negative predictive value of [¹⁸ F]CTT1057	Proportion of regions that are CTS and [18F]CTT1057 negative (TN) among those regions that test negative on [18F]CTT1057 (TN or FN)		
Evaluate the region level accuracy of [18F]CTT1057	 Proportion of regions that are CTS and [¹8F]CTT1057 positive (TP) and negative (TN) among those regions that identified on [¹8F]CTT1057 (TP, TN, FP and FN) 		
Evaluate the patient-level positive predictive value related to PSA levels	Percentage of patients who have at least one TP lesion (exactly anatomically localized correspondence between [¹8F]CTT1057 PET imaging and the reference standard), regardless of any co-existent FP findings, out of all patients who are [¹8F]CTT1057 positive, stratified by PSA levels		
Characterize the safety and tolerability of [18F]CTT1057	Incidence of AEs Treatment emergent adverse event (TEAE) rate within 14 days after each PET tracer administration		

Amended Protocol (Version No.	01 Clean)
Allieliaea i Totocoi (VEISION INC	. U i Cicaii)

Objective(s)	Endpoint(s)	
• [¹⁸ F]CTT1057 scan inter-reader variability	Inter-reader agreement of [18F]CTT1057 images	
• [¹⁸ F]CTT1057 scan intra-reader variability	Intra-reader agreement of [18F]CTT1057 images	
 Concordance between [¹⁸F]CTT1057 and [⁶⁸Ga]Ga-PSMA-11 for detection of lesions at lesion level using central reads 	Concordance between [18F]CTT1057 and [68Ga]Ga-PSMA-11 for detection of PSMA-positive lesions (location and number) using central reads	
 Evaluate the change in patient management plans attributed to the PET/CT scan 	Percentage of patients who underwent a change in intended treatment plan attributed to the PET/CT scan as assessed by pre and post imaging questionnaires	

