As this is a diagnostic study patients enrolled are not expected to derive direct benefit even though it is expected that distant disease will be identified in some patients as a consequence of this study and these patients may benefit from a more appropriate management plan, which will not be based on the investigational procedure alone, but confirmed by SoC diagnostic procedures.

The risk to participants in this trial may be minimized by compliance with the eligibility criteria and study procedures, as well as close clinical monitoring. Appropriate eligibility criteria are included in this protocol.

The risk-benefit ratio is expected to be favorable to the [18F]CTT1057 imaging agent. Additional details of the nonclinical and clinical experience with [18F]CTT1057 are provided in the IB.

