Change in patient management plans attributed to the [18F]CTT1057 PET/CT scan is defined as the percentage of patients who undergo a change in intended treatment plan attributed to the PET/CT scan as assessed by pre imaging questionnaire 1 and post imaging questionnaire 2

Numbers and percentage of patients on each category of treatment plan: surgery, radiation alone, radiation alone with change in radiation treatment plan (only applicable for questionnaire 2), radiation plus ADT, ADT alone, observation/surveillance, other (free text box) in two questionnaires will be calculated.

Treatment plan change is defined as a pair of categories (one category of questionnaire 1, one category of questionnaire 2)

Numbers and percentage of patients on the treatment change defined above will be calculated.

The following secondary endpoints, centralized imaging assessment will be used as reference standard if pathology assessment is not available for a lesion.

Region-level sensitivity is defined as the proportion of TP regions among those that are TP or FN

Region-level specificity is defined as the proportion of TN regions among those that are TN or

Region-level negative predictive value is defined as the proportion of TN regions among those that are TN or FN

Region-level accuracy is defined as the proportion of TP and TN regions among those that are identified on [18F]CTT1057 (regardless of TP, TN, FP, FN)

where TP, TN, FP, FN regions are defined as follows:

- PSMA TP regions are regions containing at least one TP lesion (anatomically localized correspondence between [18F]CTT1057 PET imaging and the CTS).
- PSMA TN regions are regions containing no lesions with pathological [18F]CTT1057 uptake and confirmed by CTS.
- PSMA FP regions are regions containing lesions with pathological [18F]CTT1057 uptake but will be verified negative by CTS or none is correctly localized in anatomical location by the CTS.
- PSMA FN regions are regions containing no lesions with pathological [18F]CTT1057 uptake but will be confirmed having at least one lesions with the CTS.

Number of TP, TN, FP, FN regions will be presented and used to calculate the diagnostic performance parameters.

95% CI for region-level diagnostic performance parameters will be calculated using logistic random-effects models taking into account the correlation among regions within one patient.

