16.4 Appendix 4: Patient Management questionnaire

A questionnaire on the planned patient management will be filled-in by the treating physician/Clinical Study Investigator before (questionnaire 1) and within 14 days after knowing the results of the [18F]CTT1057 PET/CT scan (questionnaire 2).

Options will be given in the questionnaire to capture possible management plan, such as

- Surgery
- Radiation alone
- Radiation alone with change in radiation treatment plan (only applicable for questionnaire 2)
- Radiation plus ADT
- ADT alone
- Observation/surveillance
- Other (free text box)

The results of the [¹⁸F]CTT1057 PET/CT scan will be provided to the Study Investigator before the patient undergoes the planned treatment by a local nuclear medicine physician or radiologist with expertise in reading oncology PET/CT scans, who will be blinded to [⁶⁸Ga]Ga-PSMA-11 data but not to other patient data, in order to reproduce as much as possible the real clinical context to assess the potential clinical impact of the investigational procedure.

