Change in patient management plans attributed to the [18F]CTT1057 PET/CT scan is defined as the percentage of participants who undergo a change in intended treatment plan attributed to

the PET/CT scan as assessed by pre-imaging questionnaire 1 and post-imaging questionnaire 2.

The number and percentage of participants from the F-SAF for each of the following categories of treatment plan in each of the two questionnaires will be calculated: surgery, radiation alone, radiation alone with change in radiation treatment plan (only applicable for questionnaire 2), radiation plus ADT, ADT alone, observation/surveillance, other (free text box).

Treatment plan change is defined as a change in the pair of categories (one category of questionnaire 1, one category of questionnaire 2).

The number and percentage of participants from the F-SAF with treatment plan change as defined above will be calculated. Shift tables comparing treatment plans between questionnaire 1 and 2 will be displayed. The number (%) of participants with and without a change in treatment plans by [18F]CTT1057 local read results (i.e. positive, negative, and inconclusive) will be tabulated.

**Region-level sensitivity** is defined as the proportion of TP regions among those that are TP or FN

**Region-level specificity** is defined as the proportion of TN regions among those that are TN or FP

**Region-level negative predictive value** is defined as the proportion of TN regions among those that are TN or FN

**Region-level accuracy** is defined as the proportion of TP and TN regions among those that are identified on [18F]CTT1057 (regardless of TP, TN, FP, FN)

where TP, TN, FP, FN regions are defined as follows:

- PSMA TP regions are regions containing at least one TP lesion (anatomically localized correspondence between [18F]CTT1057 PET imaging and the CTS).
- PSMA TN regions are regions containing no lesions with pathological [18F]CTT1057 uptake and confirmed by CTS.
- PSMA FP regions are regions containing lesions with pathological [F]CTT1057 uptake but are verified negative by CTS or none is correctly localized in anatomical location by the CTS.
- PSMA FN regions are regions containing no lesions with pathological [F]CTT1057 uptake but are confirmed as having at least one lesion with the CTS.

Number of TP, TN, FP, FN regions will be presented and used to calculate the diagnostic performance parameters.

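### The management-change endpoint counts every difference between the two questionnaires and cannot isolate the part due to [18F]CTT1057

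*Protocol*

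**What the plan says.** Protocol Table 2-1 defines the endpoint as "Percentage of patients who underwent a change in intended treatment plan attributed to the PET/CT scan as assessed by pre and post imaging questionnaires". Appendix 4 (Section 16.4) gives the aim of the questionnaires: "to assess the potential clinical impact of the investigational procedure".

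The counting rule is simpler. SAP Section 2.6.1 states: "Treatment plan change is defined as a change in the pair of categories", one category from each questionnaire. Protocol Section 12.5.1 likewise works from the pair of categories alone. The SAP reports the number and percentage of the F-SAF with such a change, shift tables, and change or no change by local [18F]CTT1057 read.

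On the basis for a change, Protocol Section 3 (repeated in SAP Section 1.1) says: "Any change in patient management plan between the questionnaire 1 and questionnaire 2 should not be based only on" the [18F]CTT1057 result. The next sentence reads: "Other diagnostic procedures should be performed as per SoC in order to confirm and implement the changed management plan". Protocol Section 4.5, speaking of patients who may benefit from a better plan, describes that plan as one "which will not be based on the investigational procedure alone, but confirmed by SoC diagnostic procedures".

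On timing, questionnaire 1 comes before the [18F]CTT1057 result is known and questionnaire 2 within 14 days after. Protocol Section 8.5.1 adds that in sequence 1 questionnaire 2 should be completed before the [68Ga]Ga-PSMA-11 scan. Nothing equivalent is stated for sequence 2.

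**The concern.** The endpoint carries a causal label, but the statistic is a plain before-and-after difference. The two agree only if nothing other than the [18F]CTT1057 result reaches the treating physician between the forms, or if the form records what prompted the change. The plan does not secure the first, and the documents do not describe the second.

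A change prompted by a contrast CT or by [68Ga]Ga-PSMA-11 would then be reported as clinical impact of [18F]CTT1057. This matters most for [68Ga]Ga-PSMA-11, which Protocol Section 4.1 treats as a surrogate standard of truth and which is itself likely to influence management. The Section 3 sentence adds a second difficulty. Read literally, it asks that a recorded change rest on something besides the scan to which the endpoint attributes it.

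**Working it through.** The plan states no expected rate, threshold or power for this endpoint, so there is no figure to reproduce. The check compares passages, with one piece of arithmetic for scale.

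**1. Label against rule.** The label (Protocol Table 2-1, Protocol Section 12.5.1, SAP Section 2.6.1) requires that the change be attributed to the scan. The rule requires only that the two categories differ. Neither document describes a reason-for-change item, an attribution item or adjudication. Appendix 4 lists management options only.

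**2. What can reach the physician between the two forms.** The treating physician receives local reads of standard-of-care images, including [68Ga]Ga-PSMA-11, for management decisions (Protocol Section 3).

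| Result | Sequence 1 | Sequence 2 |
|---|---|---|
| [18F]CTT1057 local read | yes, by design | yes, by design |
| Contrast CT (or MRI), bone scan, other standard-of-care imaging (within 8 weeks either side, Protocol Table 8-2) | possible | possible |
| [68Ga]Ga-PSMA-11 local read | kept out by Protocol Section 8.5.1 | possible |

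For the sequence 2 cell: [68Ga]Ga-PSMA-11 is given on Day 1 and [18F]CTT1057 at least 14 days later. A questionnaire 1 completed before Day 1 meets the timing rule, because it precedes the [18F]CTT1057 result. The [68Ga]Ga-PSMA-11 read can then become known in the interval. A questionnaire 1 completed after that read would avoid the problem, but nothing requires it.

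**3. Scale.** Planned enrolment is about 190, allocated 1:1 to sequence. 190 × 1/2 = 95 participants are in sequence 2. This is the number in whom a [68Ga]Ga-PSMA-11 result *can* fall between the forms, not an estimate of how many will be affected. The standard-of-care imaging route is open in both sequences.

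**4. What the planned tables can separate.** Tabulating change by local [18F]CTT1057 read shows whether changes cluster in scan-positive patients. It cannot show which result prompted a change when [18F]CTT1057 and another test point the same way. SAP Section 2.6.1 specifies no table by sequence for this endpoint, so the better-protected sequence 1 is pooled with sequence 2.

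**5. Size of the error.** No attribution data are described. On the documents alone, the share of counted changes not due to [18F]CTT1057 could lie anywhere from 0% to 100%.

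**6. The Section 3 sentence.** Two readings are open. If it governs the answer on questionnaire 2, a physician holding only the [18F]CTT1057 result would leave the plan unchanged or wait for other evidence. If it governs implementation, the physician records the changed intention and confirms it before acting. The sentence names the questionnaires, which favours the first reading. The sentence after it speaks of confirming and implementing a plan already changed, which favours the second, as does Section 4.5. The text does not settle the matter.

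**The case against.** The strongest reply is that the endpoint concerns the *intended* plan, and that Section 3, read with its next sentence and with Section 4.5, is patient-protection wording about acting on that plan. On that reading no intended change is suppressed and no contradiction exists. This stands as a tenable reading, and for that reason the sentence is treated here as ambiguous rather than as proof of bias.

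The design also has real safeguards. The questionnaires bracket the [18F]CTT1057 result with a short window after it. The local [18F]CTT1057 reader is blinded to [68Ga]Ga-PSMA-11. Sequence 1 has its timing rule, and change is tabulated by local read. These give partial attribution. They are incomplete because the blinding applies to the reader and not to the physician who completes the form, and because the timing rule covers one sequence only.

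The form itself is not reproduced, and its options are introduced as examples, so an attribution item cannot be excluded. If one exists, SAP Section 2.6.1 does not use it. Standard-of-care imaging findings are captured in the eCRF (Protocol Section 8.3.1), which may show that other imaging was done and what it found. As described, those data do not show what the physician knew at each questionnaire or what prompted the change.

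A reader might infer that the endpoint fails to measure its objective altogether, or that the question cannot be answered. The documents do not support that, given the safeguards above and the unseen form. Nor do they support any numerical estimate of bias, or a claim about its direction.

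**Conclusion.** The concern holds in a limited form. The statistic measures any change in intended plan between the two questionnaires. It cannot isolate the part due to [18F]CTT1057, most clearly in sequence 2 (about 95 of 190 participants) and wherever other imaging results arrive between the forms. Section 3 of the protocol and Section 1.1 of the SAP leave it unclear whether a scan-driven intention may be recorded on questionnaire 2.

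The size and direction of the error are unknown. The conclusion assumes that the form has no attribution item beyond what Appendix 4 describes, and that questionnaire 1 may be completed at any time before the [18F]CTT1057 result is known. The endpoint is descriptive, with no hypothesis or success threshold. The co-primary endpoints and the reader-based success rule do not depend on it.

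**What to change.** 1. Reconcile the sentence in Protocol Section 3 and SAP Section 1.1 with Table 2-1, Protocol Section 12.5.1 and SAP Section 2.6.1. It should be clear whether the sentence concerns the questionnaire 2 answer or implementation of the plan. The patient safeguard itself should not be altered.
2. If the form lacks them, add two items to questionnaire 2: whether the change is attributed to the [18F]CTT1057 scan, and which other imaging results have been received since questionnaire 1.
3. In SAP Section 2.6.1, report attributed changes beside all changes, and both by scan sequence.
4. For participants without the new items, do not score a change as unattributed. Report all changes by sequence under the label *change in intended plan after the [18F]CTT1057 scan*.

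The cost is one clarified sentence, two items on an existing form and some extra table rows. The attributed percentage may be lower than the all-changes percentage, and participants already enrolled contribute only to the relabelled figure. The current SAP amendment is dated 20-Dec-2023, after the dry run and before database lock, so new form items may reach few or no participants. That is an inference from the stage of the study. The by-sequence report and the relabelling need no new data and can be done in any case.
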